Appendix 7. Informed consent, Denmark

In Denmark temporarily incompetent patients will be enrolled after informed consent from two physicians, who are independent of the trial (trial guardians). As soon as possible after enrolment, consent will be obtained from the patient's next of kin and general practitioner or the Regional Medical Officer of Health according to Danish law. Patients, who regain consciousness, will be asked for informed consent as soon as possible. The process leading to the achievement of informed consent will be in compliance with all applicable regulations. The consenting party will be provided with written and oral information about the trial so he/she is able to make an informed decision about participation in the trial. The information will be given in a separate room, and the consenting party has the right to bring a companion.

Written information and the consent form will be subjected to review and approval by the relevant ethic committees.

Lack of informed consent from the general practitioner

If the general practitioner does not want to make up his/her mind about the patient's participation in the trial, e.g. if he/she does not have the knowledge to make the decision or for any other reasons the patient will continue in the trial until informed consent can be obtained from the patient him-/herself. If the general practitioner cannot be reached the Regional Medical Officer of Health will be contacted for consent.

Lack of informed consent from the patient's next of kin

If it is not possible (i.e. contact cannot be obtained) - after obtaining informed consent from two independent physicians and from the patient's general practitioner/the Regional Medical Officer of Health - to obtain informed consent from the patient's next of kin, the patient will continue in the trial until informed consent can be obtained from the patient him-/herself.

Lack of informed consent from the patient's next of kin and the patient deceases

If it is not possible (i.e. contact cannot be obtained) - after obtaining informed consent from two independent physicians and from the patient's general practitioner/the Regional Medical Officer of Health - to obtain informed consent from the patient's next of kin, the patient will continue in the trial until informed consent can be obtained from the patient him-/herself. If the patient deceases before informed consent is obtained, or remains in a permanent state of incompetence, the collected data will be kept and trial outcomes will be collected centrally.

Deviation from the standard informed consent

According to the standard informed consent form from the National Ethics Committee regarding competent patients, the patient can choose not to receive information about the data collected during the trial. However, the purpose of this trial is not to generate new knowledge about the specific patient, so we find that this question is redundant, and have omitted the question from the consent form to spare the patient from making unnecessary decisions.

Appendix 7.1 Informed consent, Denmark (Amendment 1):

Amendment to the previously approved protocol entitled ‘Stress ulcer prophylaxis with proton pump inhibitor (pantoprazole) in adult critically ill patients in the intensive care unit: A randomised, blinded, placebo-controlled trial’, version 3.0, October 20th 2015

This amendment replaces Appendix 7 in the above mentioned protocol.

In Denmark temporarily incompetent patients will be enrolled after informed consent from one physician, who is independent of the trial (trial guardians). As soon as possible after enrolment, consent will be obtained from the patient’s next of kin. Patients, who regain consciousness, will be asked for informed consent as soon as possible. The process leading to the achievement of informed consent will be in compliance with all applicable regulations. The consenting party will be provided with written and oral information about the trial so he/she is able to make an informed decision about participation in the trial. The information will be given in a separate room, and the consenting party has the right to bring a companion.

Written information and the consent form will be subjected to review and approval by the relevant ethic committees.

Lack of informed consent from the patient’s next of kin

If information about the patient’s next of kin is not available after inclusion the investigator will seek information from e.g. the patient’s general practitioner, the police, nursing homes etc. In these situations it may take 1-2 weeks to conclude that no next of kin can be identified. If no one is identified and the patient remains incompetent the trial intervention will be discontinued. All initiatives to identify the patient’s next of kin will be documented in patient files, logs or similar.

Lack of informed consent from the patient’s next of kin and the patient deceases

If the patient deceases before informed consent has been obtained (due to rapid progression of critical illness or because the patient’s next of kin is not yet identified) and the patients has been correctly included in the trial, collected data will be kept for analysis.

Deviation from the standard informed consent

According to the standard informed consent form from the National Ethics Committee regarding competent patients, the patient can choose not to receive information about the data collected during the trial. However, the purpose of this trial is not to generate new knowledge about the

specific patient, so we find that this question is redundant, and have omitted the question from the consent form to spare the patient from making unnecessary decisions.

Appendix 7.2 Informed consent, Denmark (Amendment 2):

Amendment to the previously approved protocol entitled ‘Stress ulcer prophylaxis with proton pump inhibitor (pantoprazole) in adult critically ill patients in the intensive care unit: A randomised, blinded, placebo-controlled trial’, version 3.0, October 20th 2015

This amendment replaces amendment 7.1 to the above mentioned protocol.

In Denmark temporarily incompetent patients will be enrolled after informed consent from one physician, who is independent of the trial (first trial guardian). As soon as possible after enrolment, consent will be obtained from the patient’s next of kin and a second physician (second trial guardian). The second trial guardian must be different from the first trial guardian, but also independent of the trial. Patients, who regain consciousness, will be asked for informed consent as soon as possible. The process leading to the achievement of informed consent will be in compliance with all applicable regulations. The consenting party will be provided with written and oral information about the trial so he/she is able to make an informed decision about participation in the trial. The information will be given in a separate room, and the consenting party has the right to bring a companion.

Written information and the consent form will be subjected to review and approval by the relevant ethic committees.

Lack of informed consent from the patient’s next of kin

If information about the patient’s next of kin is not available after inclusion the investigator will seek information from e.g. the patient’s general practitioner, the police, nursing homes etc. In these situations it may take 1-2 weeks to conclude that no next of kin can be identified. If no one is identified and the patient remains incompetent the trial intervention will be discontinued. All initiatives to identify the patient’s next of kin will be documented in patient files, logs or similar.

Lack of informed consent from the patient’s next of kin and the patient deceases

[figure not shown]
If the patient deceases before informed consent has been obtained (due to rapid progression of critical illness or because the patient’s next of kin is not yet identified) and the patient has been correctly included in the trial, collected data will be kept for analysis.

Deviation from the standard informed consent

According to the standard informed consent form from the National Ethics Committee regarding competent patients, the patient can choose not to receive information about the data collected

during the trial. However, the purpose of this trial is not to generate new knowledge about the specific patient, so we find that this question is redundant, and have omitted the question from the consent form to spare the patient from making unnecessary decisions.

Appendix 8. Timeline

Appendix 9. SAPS II scoring sheet [74]

Part 1

Variable	Points:	26	13	12	11	9	7	6	5	4	3	2	0
Age													< 40
Heart rate					< 40							40-69	70-119
Systolic blood pressure mmHg			< 70							70-99			100-199
Body temperature													
°C													< 39
°F													<102.2
Only if ventilated													
PaO ₂ mmHg/FiO ₂					< 100	100-199			≥200				
PaO ₂ kPa/FiO ₂					<13.3	13.3-26.5			≥26.6				
Urinary output ml/day					<500					500-999			> 1000
Serum urea level													
mmol/l													< 10.0
(g/dl)													(< 0.6)
WBC					<1.0								1.0-19.9
10 ⁹ /l													
Serum potassium												<3.0	3.0-4.9
mmol/l													
Serum sodium mmol/l									<125				125-144
Serum bicarbonate mEq/l									<15		15-19		≥20
Bilirubin													
umol/l													< 68.4
(mg/dl)													(<4.0)
Glascow coma scale score	<6	6-8					9-10		11-13				14-15
Chronic disease													
Type of admission													Scheduled surgical

Part 2

Variable	1	2	3	4	6	7	8	9	10	12	15	16	17	18
Age						40-59				60-69	70-74	75-79		≥80
Heart rate				120-159		≥160								
Systolic blood pressure mmHg		≥200												
Body temperature °C			≥39.0											
°F			≥102.2											
Only if ventilated PaO ₂ mmHg/FiO ₂														
PaO ₂ kPa/FiO ₂														
Urinary output ml/day														
Serum urea level mmol/l (g/dl)					10.0-29.9 (0.60-1.79)				≥30.0 (≥1.80)					
WBC 10 ⁹ /l			≥20.0											
Serum potassium mmol/l			≥5.0											
Serum sodium mmol/l	≥145													
Serum bicarbonate mEq/l														
Bilirubin umol/l (mg/dl)				68.4-102.5 (4.0-5.9)				≥102.6 (≥6.0)						
GCS score														
Chronic disease								Metastatic cancer	Hematologic malignancy				AIDS	
Type of admission					Medical		Unscheduled surgical							
Sum of points														

Appendix 10. SOFA score [75]

	0	1	2	3	4
Respiration PaO ₂ /FiO ₂ (mmHg)	≥ 400	< 400	< 300*	< 200 [†]	< 100 [†]
(KPa)	≥ 53	< 53	< 40*	< 27 [†]	< 13 [†]
Coagulation Platelets (x 10 ³ /mm ³)	≥ 150	101-150	51-100	21-50	≤ 20
Liver Bilirubin (mg/dl)	< 1.2	1.2-1.9	2.0-5.9	6.0-11.9	> 12.0
(umol/l)	< 20	20-32	33-101	102-204	> 204
Cardiovascular Hypotension* (MAP)	≥ 70	< 70	Dopamine ≤ 5 [⊛] OR Dobutamine (any dose) OR Milirone (any dose) OR Levosimendan (any dose) OR	Dopamine ≥ 5 [⊛] OR Norepinephrine ≤ 0.1 [⊛] OR Adrenaline ≤ 0.1 [⊛] OR Vasopression (any dose) OR Phenylephrine (any dose) OR	Dopamine > 15 [⊛] OR Norepinephrine > 0.1 [⊛] OR Adrenaline > 0.1 [⊛]
CNS Glasgow coma scale score	15	13-14	10-12	6-9	< 6
Renal Creatinine (mg/dl)	< 1.2	1.2-1.9	2.0-5.9	6.0-11.9	>12.0
(umol/l)	< 110	110-170	171-299	300-440	>440
OR Urine output				<500 ml/day	<200 ml/day

* without respiratory support

[†] with respiratory support

[⊛] Adrenergic agents administered for at least one hour (doses given are in ug/kg/min).

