The Simplified Acute Physiology Score (SAPS II) [74] (*appendix 9*) is based on the most extreme (highest or lowest) values from 24 hours prior to randomisation. The score consists of 17 variables: 12 physiologic variables, age, type of admission and 3 variables related to underlying disease to give a total score ranging from 0 to 163, with higher scores indicating greater severity of illness. The score will be calculated from data from the 24 hours prior to randomisation

The Sequential Organ Failure Assessment (SOFA) Score [75] (*appendix 10*) will be calculated from raw physiology and treatment data from the 24 hours prior to randomisation. The SOFA Score consists of weightings for six organ systems to give a total score ranging from 0 to 24, with higher scores indicating a greater degree of organ failure.

Definition of daily collected variables:

Delivery of trial medication: confirmation of administration of the trial drug

Treatment with PPI or H2RA: prescription of any of these drugs in any dose (major protocol violation if the treatment is initiated (e.g. as prophylaxis) without clinical indication (e.g. gastrointestinal bleeding))

Mechanical ventilation: invasive and non-invasive mechanical ventilation including continuous mask CPAP or CPAP via a tracheotomy. Intermittent CPAP is NOT mechanical ventilation.

Circulatory support: continuous infusion of vasopressor or inotrope (norepinephrine, epinephrine, phenylephrine, vasopressin or dopamine, dobutamine, milirinone or levosimendan)

Renal replacement therapy: any form of renal replacement therapy on this day. In patients receiving intermittent renal replacement therapy days between treatments are included

Clinically important GI bleeding, onset of pneumonia, CDI, and acute myocardial ischemia in the ICU are defined as outcomes

Treatment with enteral feeding: any dose of enteral feeding (including oral nutritional intake) during the day

Units of red blood cells: cumulated number of units of red blood cells transfused during the day

Serious adverse reactions (SARs) are defined below

Definition of bleeding variables:

Confirmed diagnosis: diagnosis/origin of bleeding confirmed by endoscopy or other method

Verification of ulcer/gastritis/bleeding oesophageal varices: confirmation of one of the three specific diagnoses by endoscopy or other method

Haemostasis achieved or attempted: documentation in patient charts of haemostasis achieved or attempted by endoscopy, open surgery or coiling

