The secondary analysis will be a multiple logistic regression analysis of the ITT population adjusted for stratification variables and additionally differences in potential confounders: age, SOFA score at baseline, and type of admission (medical, elective surgery or emergency surgery). Intervention group and the stratification variable haematological cancer are regarded as fixed effects and trial site is regarded as random effects in the model. Furthermore, frequencies and percentages per group will be reported and an unadjusted Chi-square test for differences in the primary outcome will be provided.

Pre-defined subgroup analyses (see former section) of the ITT population will be conducted using logistic regression analysis adjusted for stratification variables.

A sensitivity analysis of the primary outcome measure including the per-protocol population will be conducted. The per-protocol population will be all randomised patients except those having one or more protocol violations defined as:

- Patients who did not receive the allocated trial intervention at all
- Patients who did not receive the trial intervention for at least two days in a row
- Patients who received treatment (open label) with PPI or histamine-2-receptor antagonists except for those receiving it according to the protocol (i.e. occurrence of GI bleeding after randomisation).
- Patients who withdrew from trial intervention, but consented to the use of data
- Monitoring revealed that one or more in- or exclusion criteria were violated

Secondary outcome measures

The secondary outcomes will only be analysed in the ITT population. The primary analysis of the binary secondary outcome measures will be a logistic regression analysis adjusted for the stratification variables (site and presence of haematological cancer). Results will be presented as odds ratios and relative risk ratios.

Furthermore, frequencies and percentages per group will be reported and an unadjusted Chi-square test for differences in the primary outcome will be provided.

The primary analysis of rate data ('Percentage of days alive without life support in the 90-day period') will be a generalized linear model (initially Poisson distribution, alternatively negative binomial).²⁸ If the assumptions for Poisson distribution or negative binomial distribution are not met, data will be analysed using the non-parametric Van Elteren test adjusted for site, but no other variables.²⁹

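### Appendix 10 (SOFA): the creatinine limits in mg/dl contradict those in umol/l at scores 3 and 4, so the same creatinine can score 1 to 2 points lower on the mg/dl row

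*Combined protocol and SAP*

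**What the plan says.** In Appendix 10 the row beginning "Renal Creatinine (mg/dl" reads in full "Renal Creatinine (mg/dl) < 1.2 1.2-1.9 2.0-5.9 6.0-11.9 >12.0" for scores 0 to 4, and directly below, in the second unit, "umol/l) < 110 110-170 171-299 300-440 >440". The liver component reads "Liver Bilirubin (mg/dl) < 1.2 1.2-1.9 2.0-5.9 6.0-11.9 > 12.0" and "umol/l) < 20 20-32 33-101 102-204 > 204". The original and the amended protocol print the same values. The three amendments concern Danish consent and the DMSC charter; none touches this table.

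Appendix 4 says that SOFA "will be calculated from raw physiology and treatment data from the 24 hours prior to randomisation", and refers to Appendix 10 for the scoring. Protocol section 9.2.2 lists plasma creatinine among the variables collected for this purpose, without a unit.

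Baseline SOFA is then used in two places:
- In the secondary adjusted analyses (protocol section 11.2; SAP, Primary outcome measure and Secondary outcome measures), where the added covariates are "age, SOFA score at baseline, and type of admission".
- In the list of imputation predictors in the SAP section on missing data, which applies when more than 5% of observations are missing for an analysis.

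**The concern.** The two creatinine rows are offered as the same scale in different units, so a patient should get the same score from either. They cannot both be right, because the five mg/dl bands for creatinine are those for bilirubin, a different analyte with a different conversion.

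At stake is the definition of a pre-specified prognostic covariate. The patients exposed to the conflict are those with high creatinine, and the trial enrols such patients by design, since renal replacement therapy is a qualifying risk factor (section 4.1). The plan does not state the unit in which creatinine is recorded at each site, or which row the scoring program uses. If values in mg/dl were scored on the mg/dl row, severity would be understated in those patients, and the error could differ between sites.

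**Working it through.** **Inputs.** The lower limits of scores 1 to 4 in Appendix 10 (for score 4, the value that must be exceeded). The only outside figure is the creatinine conversion factor, taken as 88.4 umol/l per mg/dl. The documents do not give it. The range used is 85.5 to 91.7, which is what the table's own cut-offs for scores 2 and 1 imply.

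**Step 1: is the ratio constant?** Factor = umol/l limit / mg/dl limit.

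| Score | Bilirubin | Creatinine |
|---|---|---|
| 1 | 20/1.2 = 16.7 | 110/1.2 = 91.7 |
| 2 | 33/2.0 = 16.5 | 171/2.0 = 85.5 |
| 3 | 102/6.0 = 17.0 | 300/6.0 = 50.0 |
| 4 | 204/12.0 = 17.0 | 440/12.0 = 36.7 |

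The bilirubin rows agree within rounding. The SAPS II sheet (Appendix 9) supports them: 68.4/4.0 = 17.1 and 102.6/6.0 = 17.1. The creatinine rows agree roughly at scores 1 and 2 and then part. No single factor fits all four cut-offs, so this step needs no outside figure.

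**Step 2: how far apart are the limits?**
- The printed mg/dl limits in umol/l: 6.0 x 88.4 = 530 (513 to 550 over the range) and 12.0 x 88.4 = 1061 (1026 to 1100). The umol/l row has 300 and 440.
- The printed umol/l limits in mg/dl: 300/88.4 = 3.4 (3.3 to 3.5) and 440/88.4 = 5.0 (4.8 to 5.1). The mg/dl row has 6.0 and 12.0.

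**Step 3: score the same creatinine on both rows.** Values in mg/dl are rounded to one decimal. The table leaves exactly 12.0 mg/dl unassigned; it is counted here as score 3.

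| Creatinine at factor 88.4 | umol/l row | mg/dl row | Difference |
|---|---|---|---|
| 300-440 umol/l (about 3.4-4.9 mg/dl) | 3 | 2 | -1 |
| 441-525 umol/l (about 5.0-5.9 mg/dl) | 4 | 2 | -2 |
| 526-1065 umol/l (6.0 to about 12 mg/dl) | 4 | 3 | -1 |
| 1066 umol/l and above | 4 | 4 | 0 |

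At factor 85.5 the 2-point band is 441-508 umol/l; at 91.7 it is 441-545. The largest gap is 2 points at both ends of the range.

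Near the lower cut-offs there are only narrow 1-point differences. At 88.4, 102-109 umol/l scores 1 higher on the mg/dl row and 171-172 scores 1 lower. These come from rounding of the limits and are not part of the point.

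**The case against.** The strongest objection is that little depends on this table, and most of that stands.

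- **Primary analysis.** A reader might infer that the main result is affected, because the primary analysis is itself an adjusted one. It adjusts only for site and haematological cancer. SOFA is not an eligibility criterion, an outcome or a subgroup variable; the severity subgroup uses SAPS II. One conditional route remains: the SAP bases the primary result on imputed data if imputation is used, and SOFA is then a predictor.
- **Scoring at sites.** A reader might picture staff scoring patients from this sheet. The protocol says that SOFA is calculated from collected raw data. This does not remove the conflict, since the calculation must still use one row and none is named, but nothing shows that mg/dl values exist or that the mg/dl row is applied.
- **Bias.** A reader might infer a biased treatment effect. The values precede randomisation and allocation is concealed, so an error in this score has no reason to differ by arm. The plausible cost is slightly weaker adjustment in a secondary model and a baseline score that cannot be reproduced.
- **Urine output.** The renal component can also be set by urine output: below 500 ml/day gives 3 and below 200 ml/day gives 4. In oliguric patients this can hide part or all of the gap.
- **Source of the error.** That the bilirubin cells were copied is a strong inference, but the documents show only that the cells are identical. They also do not prove the umol/l row correct; the cited SOFA source is needed for that.

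None of this answers the contradiction itself.

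**Conclusion.** The point holds as an error in a scoring definition. The limits for scores 3 and 4 conflict under any conversion factor. The resulting gap is at most 2 of the 24 SOFA points, in a band about 1 mg/dl wide, and 1 point on either side of it.

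The sizes assume 88.4 umol/l per mg/dl (85.5 to 91.7) and a renal score set by creatinine. The direction, with the mg/dl row scoring too low, takes the umol/l row as the reference. Any practical effect further requires creatinine to be held in mg/dl and scored on that row, and the plan does not say whether that happens at any site. The documents support no claim about the primary estimate or about bias between the arms. It is a small defect, worth correcting because the correction is simple.

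**What to change.** 1. Reconcile the two creatinine rows in Appendix 10 against the cited SOFA source. Either delete the mg/dl row, or replace its upper limits with values that match the umol/l row: score 3 from about 3.4 mg/dl (3.3 to 3.5) and score 4 above about 5.0 mg/dl (4.8 to 5.1).
2. State the unit of creatinine in the data collection list, and convert all values to umol/l before the renal component is calculated.
3. Check that the scoring code uses the umol/l row. If any scores were derived from the mg/dl row, recalculate them from the raw creatinine.

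The cost is one table correction and one check of the scoring code. No new data are needed, because raw creatinine is already collected.

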Appendix 11. Power estimation

All power estimations have been calculated on data from the international SUP-ICU 7-day inception cohort study[57].

Since we do not know whether treatment with acid suppressants reduce or increase mortality, a number of scenarios have been considered (+/- 20 relative risk reduction):

1) 25.0% mortality 90 days after inclusion among patients with:

At least one risk factor*

No acid suppressants at ICU admission

Treatment with acid suppressants during ICU admission

No clinically important bleeding** during ICU admission

Power estimations:

ARR	Power	Patients per group
- 5%	80%	1091
	90%	1461
+ 5%	80%	1248
	90%	1671

We do not know whether PPI benefits or harms the patients, and need to include both scenarios. With 1671 patients in each group we will be able to show an absolute increase in risk of 5% with 90% power at the primary outcome, but also an absolute risk reduction of 5% with 90% power. The sample size has been calculated on patients fulfilling inclusion and exclusion criteria in the SUP-ICU trial and because few patients were not treated with acid suppressants during ICU admission, the estimation is based on the group receiving acid suppressants (intervention group)

2) 25.9% mortality 90 days after inclusion among patients with:

At least one risk factor*

No acid suppressants at ICU admission

Treatment with acid suppressants during ICU admission

Bleeding (overt or clinically important**) or no bleeding during ICU admission

Power estimations:

ARR	Power	Patients per group
- 5,2%	80%	1034
	90%	1384
+5,2%	80%	1180
	90%	1579

3) 29.2% mortality 90 days after inclusion among patients with:

At least one risk factor*

Acid suppressants and no acid suppressants at ICU admission

Treatment with acid suppressants during ICU admission

No bleeding (overt or clinically important**) during ICU admission

Power estimations:

ARR	Power	Patients per group
- 5,8%	80%	901
	90%	1206
+5,8%	80%	1014
	90%	1357

4) 30.5% mortality 90 days after inclusion among patients with:

At least one risk factor*

Acid suppressants or no acid suppressants at ICU admission

Treatment with acid suppressants during ICU admission

Bleeding (overt or clinically important**) or no bleeding during ICU admission

Power estimations:

ARR	Power	Patients per group
- 6,1%	80%	837
	90%	1120
+6,1%	80%	937
	90%	1254

*Risk factors are: shock, renal replacement therapy, coagulopathy and coagulopathy and liver disease as comorbidities)

[figure not shown]
** Overt bleeding is defined as any episode of hematemesis, coffee ground emesis, melena, hematochezia or bloody nasogastric aspirate in the ICU.

Clinically significant bleeding is defined as overt bleeding and at least one of the following four features within 24 hours of GI bleeding (in the absence of other causes) [1, 5, 10] in the ICU

- e. spontaneous drop of systolic blood pressure, mean arterial pressure or diastolic blood pressure of 20 mmHg or more
- f. start of vasopressor or a 20% increase in vasopressor dose
- g. decrease in haemoglobin of at least 2 g/dl (1.24 mmol/l)
- h. transfusion of 2 units of packed red blood cells or more

